3.0 Endpoints

Below are the definitions of the endpoints used in the efficacy analysis:

- **Clinical remission:** average daily SF ≤ 2.8 and not worse than baseline AND average daily AP score ≤ 1 and not worse than baseline
- **Enhanced clinical response:** $\geq 60\%$ decrease in average daily SF and/or $\geq 35\%$ decrease in average daily AP score and both not worse than baseline, and/or clinical remission
- **Clinical response:** $\geq 30\%$ decrease in average daily SF and/or $\geq 30\%$ decrease in average daily AP score and both not worse than baseline
- **Endoscopic response:** decrease in SES-CD $> 50\%$ from baseline (or for subjects with isolated ileal disease and a baseline SES-CD of 4, at least a 2 point reduction from baseline), as scored by central reviewer

- **Ulcer-free endoscopy:** SES-CD ulcerated surface subscore of 0 in subjects with SES-CD ulcerated surface subscore ≥ 1 at baseline, as scored by a central reviewer
- **Endoscopic remission:** SES-CD ≤ 4 and at least a 2 point reduction versus baseline and no subscore greater than 1 in any individual variable, as scored by a central reviewer
- **CDAI clinical response:** reduction of CDAI ≥ 100 points from baseline
- **CDAI clinical remission:** CDAI < 150
- **SF remission:** average daily SF ≤ 2.8 and not worse than baseline
- **AP remission:** average daily AP score ≤ 1 and not worse than baseline

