 - Markov Chain Monte Carlo (MCMC) will be first applied to augment data into monotonic missing pattern, where applicable, and PROC MI will be used to generate 30 datasets using the regression method. If the binary endpoints are derived from the continuous variables, PROC MI will be applied to the continuous variables. The variables to be included in the imputation model are: treatment group, randomization stratification factors (Number of prior biologics failed (0, 1, > 1), baseline steroid use (Yes, No)), age, gender, weight and if applicable, baseline measurement and post-baseline measurements at each visit up to the end of the analysis period. The random seed for MCMC and the random seed for PROC MI are specified in [Appendix H](#). The imputed post-baseline measurements will be rounded to the same precision as the observed data before the determination of responder status. Prior to applying CMH model, subjects will be characterized as responders or non-responders based on MI imputed values if missing due to Covid-19, otherwise subjects will be considered as non-responder for missing due to other reasons in the NRI-C approach. Using the CMH model adjusted by randomization stratification factors, the endpoints will be analyzed using each of the 30 imputed datasets. SAS PROC MIANALYZE will be used to generate the final inferences of the risk difference between the risankizumab treatment group and placebo group, using Rubin's rule. The CD-related corticosteroid censoring rule, as specified in [Section 8.2.2](#) and [Appendix J](#), will be applied before and after applying MI for efficacy assessments.

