Appendix E. Simple Endoscopic Score – CD (SES-CD)

SES-CD is calculated based the sum of individual segment values for four endoscopic variables (presence and size of ulcers, ulcerated surface, affected surface and presence of narrowing). Each variable in each segment be scored 0 to 3 resulting in SES-CD values ranging from 0 to 56 with higher scores indicating more severe disease.

| Variable | Score | | | |
|------------------------|--------------------|------------------------------------|-------------------------------|---------------------------------|
| | 0 | 1 | 2 | 3 |
| Size of ulcers (cm) | None | Aphthous ulcers (diameter 0.1–0.5) | Large ulcers (diameter 0.5–2) | Very large ulcers (diameter >2) |
| Ulcerated surface (%) | None | <10 | 10–30 | >30 |
| Affected surface (%) | Unaffected segment | <50 | 50–75 | >75 |
| Presence of narrowings | None | Single, can be passed | Multiple, can be passed | Cannot be passed |

* Total SES-CD: sum of the values of the 4 variables for the 5 bowel segments. Values are given to each variable and for every examined bowel segment (for example, rectum, left colon, transverse colon, right colon and ileum).

Medscape Source: Nat Rev Gastroenterol Hepatol ©2009 Nature Publishing Group

SES-CD Scoring:

[figure not shown]
| | Rectum | Sigmoid and Left Colon | Transverse Colon | Right Colon | Ileum | Total |
|--|--------|------------------------|------------------|-------------|-------|-------|
| Size of Ulcers Enter: 0 if none 1 if aphthous ulcers (Ø 0.1 to 0.5 cm) 2 if large ulcers (Ø 0.5 to 2 cm) 3 if very large ulcers (Ø > 2 cm) | | | | | | |
| Ulcerated Surface Enter: 0 if none 1 if < 10% 2 if 10% – 30% 3 if > 30% | | | | | | |
| Affected Surface Enter: 0 if unaffected segments 1 if < 50% 2 if 50% – 75% 3 if > 75% | | | | | | |

| | Rectum | Sigmoid and Left Colon | Transverse Colon | Right Colon | Ileum | Total |
|--|---------------|-----------------------------------|-----------------------------|------------------------|----------------|--------------|
| Presence of Narrowing Enter: 0 if none 1 if single, can be passed 2 if multiple, can be passed 3 if cannot be passed | | | | | | |
| | | | | | TOTAL = | |

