Appendix H. Random Seeds

In case of non-convergence, the random seed will be updated by adding 100000 at each attempt until convergence of model happens.

Table H-1. Random Seeds for NRI-C

| Variables | Random Seed | |
|--------------------------------------|----------------|---------|
| | MCMC Procedure | PROC MI |
| CDAI | 50001 | 60001 |
| SES-CD (for 20 individual variables) | 50002 | 60002 |
| SF score | 50003 | 60003 |
| AP score | 50004 | 60004 |
| EIM | 50005 | 60005 |
| FACIT-Fatigue | 50006 | 60006 |
| IBDQ total score | 50009 | 60009 |
| PGIS | 50010 | 60010 |
| PGIC | 50011 | 60011 |

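### NRI-C imputes the 20 ordinal SES-CD items by linear regression with rounding, which biases endoscopic remission and ulcer-free endoscopy downward among COVID-19-imputed subjects, with a small whole-trial effect

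*SAP*

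**What the plan says.** SAP Section 8.3.1 (Categorical Endpoints) makes NRI-C the primary approach for binary endpoints. Subjects with a missing evaluation count as non-responders, except that data missing because of COVID-19 are multiply imputed. After an MCMC step to reach a monotone pattern, "PROC MI will be used to generate 30 datasets using the regression method". On the level of imputation: "If the binary endpoints are derived from the continuous variables, PROC MI will be applied to the continuous variables". On post-processing: "The imputed post-baseline measurements will be rounded to the same precision as the observed data before the determination of responder status".

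Table H-1 in Appendix H lists the imputed variable as "SES-CD (for 20 individual variables", that is, four endoscopic variables in five bowel segments. Appendix E gives the scale: "Each variable in each segment be scored 0 to 3".

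Section 3.0 then derives endpoints that depend on item patterns as well as on the total. Endoscopic remission needs, among other conditions, "no subscore greater than 1 in any individual variable". Ulcer-free endoscopy is "SES-CD ulcerated surface subscore of 0 in subjects with SES-CD ulcerated surface subscore ≥ 1 at baseline". Section 3.0 does not say whether that subscore is judged in each segment or summed over segments.

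The SAP gives no minimum, maximum, truncation, ordinal method or matching method for these items. It also does not say whether the 20 items enter one model or 20 models.

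**The concern.** The PROC MI regression method draws from a normal linear model. A draw rounds to 0 only if it falls between -0.5 and 0.5. Items that are 0 in most healed segments therefore come out as -1, 1 or 2 much of the time, and some come out as 4. An endpoint that needs several items to be 0, or all 20 to be at most 1, will be met too rarely in imputed subjects.

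NRI-C is the primary approach for endoscopic response (co-primary in both protocols), endoscopic remission (ranked 9th in the US list, 8th in the global list), ulcer-free endoscopy (11th and 10th) and the composites that include endoscopic response. Section 8.3 says the imputation is meant to give reliable estimates of what would have been seen without the pandemic. If the imputed patterns are systematically too unhealed, it does not do so for the pattern-based endpoints.

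**Working it through.** **1. The plan's own figure.** Section 2.4 gives 99% power for endoscopic response, 25.5% against 8%, with 342 and 171 subjects, Fisher's exact test, two-sided 0.025. Exact enumeration gives 99.8%, which agrees. The SAP gives no figure for the imputation itself.

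**2. Simulation set-up.** Five segments by four integer items (0-3), eligible SES-CD at least 6, with 684 active and 171 placebo subjects observed. The imputed set was 4,000 active-type subjects with every Week 12 item missing. Items were imputed by normal linear regression with posterior draws, then rounded. Covariates were treatment and baseline items; strata, age, gender and weight were left out. There were 26 configurations (four assumed disease patterns, several healing levels, joint or separate item models). The SAP gives no item distributions, so all of these are assumptions.

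**3. One configuration in full** (many segments involved, mean baseline SES-CD 22.5; percent of imputed subjects):

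| | Response | Remission | Ulcer-free, every segment 0 | Ulcer-free, sum 0 |
|---|---|---|---|---|
| Truth (joint run) | 39.5 | 19.4 | 16.7 | 16.7 |
| Joint model, rounded | 35.6 | 10.8 | 0.3 | 5.8 |
| Joint model, then clipped to 0-3 | 21.4 | 6.6 | 3.6 | 3.6 |
| Joint model, redrawn within 0-3 | 3.0 | 0.0 | 0.1 | 0.1 |
| Truth (separate run) | 39.4 | 19.1 | 16.3 | 16.3 |
| Separate models, rounded | 15.8 | 1.3 | 0.2 | 4.2 |

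Ratios to truth under the joint model: response 35.6/39.5 = 0.90; remission 10.8/19.4 = 0.56; ulcer-free by sum 5.8/16.7 = 0.35. Under separate models: 15.8/39.4 = 0.40; 1.3/19.1 = 0.07; 4.2/16.3 = 0.26.

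**4. All 26 configurations, unbounded and rounded.**
- Endoscopic remission was too low in 26 of 26: 48-67% of the true rate with joint models, 3-35% with separate models.
- Ulcer-free endoscopy (true 6-43%) was 0.1-1.8% if every ulcerated-surface item must equal 0, and 0.3-10.5% if values at or below 0 count as 0. It was 2-14%, or 23-64% of the true rate, if only the sum must be 0.
- Endoscopic response was too low in 23 of 26: 0.87-1.05 times the truth with joint models, 0.10-1.01 times with separate models. Allowing for other checks, I put the joint range at about 0.8-1.05.
- Clipping after rounding gave response 0-41% against a true 17-61%. Redrawing within 0-3 gave response 0-9%, remission 0-2% and ulcer-free 0-1.5%. Negative errors had been offsetting positive ones in the total; bounding removes that offset.

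**5. Both arms.** A separate simulation (assumed mean baseline SES-CD 14.5), placebo/active: true remission 8%/22% became 5%/12%, and true ulcer-free 5%/15% became 0.2%/0.3% on the every-segment reading. Response went from 13%/32% to 12%/29%. The difference among imputed subjects therefore went from 14 to 7 points for remission and from 19 to 17 for response.

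**6. Whole-trial effect.** Let f be the share imputed for COVID-19 (not in the SAP; assumed 1-10%). Trial difference = (1 - f) × true difference + f × imputed difference. Taking the extreme in which every imputed subject is a non-responder, 17.5 × (1 - f) is:

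| f | Response difference (points) | Power |
|---|---|---|
| 1% | 17.3 | 99.8% |
| 3% | 17.0 | 99.75% |
| 5% | 16.6 | 99.7% |
| 10% | 15.8 | 99.5% |

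For ulcer-free endoscopy with assumed true rates of 23.5% and 8%, imputed as 0.5% and 0.2%, f = 10% gives 0.9 × 15.5 + 0.1 × 0.3 = 14.0 points instead of 15.5.

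**7. Check of a remedy.** Predictive mean matching on the predicted Week 12 total, drawing a donor's whole 20-item vector within arm, was run for one disease pattern at four healing levels. Response was 18.2, 31.6, 45.7 and 61.5% against a true 18.0, 32.0, 46.3 and 60.1%. Remission was 10.2, 17.5, 27.7 and 39.9% against 9.6, 18.1, 28.5 and 39.0%. Ulcer-free was 8.9, 15.1, 24.1 and 34.7% against 7.9, 15.1, 24.4 and 34.0%.

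**The case against.** The strongest reply is that little turns on this. Only COVID-19-missing subjects are imputed. The extreme in which all of them fail is exactly NRI-NC, a planned sensitivity analysis for the co-primary endpoints and most binary secondary endpoints. The direction is generally conservative. An as-observed analysis is also planned. This stands as to the trial's conclusions. It does not make the stated rule sound for its purpose. Where ulcer-free endoscopy is hardly ever imputed, NRI-C nearly equals NRI-NC and comparing the two tells the reader little. The as-observed analysis also drops the steroid rule, so it does not isolate the imputation.

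The simulations use assumed item distributions and omit some listed covariates. They show a mechanism and its direction, and do not size it for this trial.

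Three stronger readings are tempting and not supported:
- A reader might infer that the co-primary result is endangered. Under unbounded joint imputation, response is close to the truth. The large losses need clipping or separate item models, neither of which the SAP prescribes.
- A reader might infer that an ulcer-free endoscopy can almost never be imputed. That holds only if every segment must be 0, and Section 3.0 leaves this open.
- A reader might infer from the predictor list and the separate SF and AP seeds that the imputation fails under MAR. Section 8.3 takes COVID-19 missingness to be unrelated to the unobserved values, so fewer predictors mainly cost precision. A seed table does not fix the model structure.

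**Conclusion.** The point holds in limited form. Linear regression with rounding on four-level items biases endoscopic remission and ulcer-free endoscopy downward among imputed subjects. That was so in every configuration run and on each reading of the ulcerated surface subscore. Co-primary endoscopic response is modestly affected as the rule is written, but depends heavily on two choices the SAP does not make: how out-of-range items are handled, and whether the items are modelled jointly. That the draws are unbounded is read from the SAP's silence, not from a stated choice.

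At trial level the bias is small and generally conservative, and it does not threaten the co-primary conclusion. These sizes rest on assumed item distributions and an assumed 1-10% of endoscopies imputed. The change is worth making because it is cheap and because the obvious repair, clipping to 0-3, makes the bias worse.

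**What to change.** In Section 8.3.1 and Appendix H, exempt SES-CD from item-level linear regression and adopt one of the following for endoscopies missing because of COVID-19:

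- impute each endoscopic responder indicator by logistic regression; or
- use predictive mean matching within arm and take one donor's complete observed 20-item vector, so that every imputed endoscopy is a real pattern on the 0-3 scale.

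In checking, both came much closer to the true rates than the planned rule; the figures shown above are for the second. The second also keeps response, remission and ulcer-free status consistent within a subject, which separately imputed indicators need not. Do not simply clip or bound the items.

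State in Section 3.0 whether the ulcerated surface subscore is per segment or summed. Keep the 30 imputations, the corticosteroid rule before and after imputation, and Rubin's rule. The cost is a few lines of SAP text and a programming change; no new data are needed.

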8.3.2 Continuous Endpoints

For continuous efficacy endpoints where Mixed-Effect Model Repeat Measurement (MMRM) analysis or Analysis of Covariance (ANCOVA) is performed, missing data will be handled using the following approaches.

- **Mixed-Effect Model Repeat Measurement (MMRM):** The repeat measurement analysis will be conducted using a mixed model including observed measurements at all post-baseline visits, after the CD-related corticosteroids censoring rule is applied (see Section 8.2.2 and Appendix J). The mixed model includes the categorical fixed effects of treatment, visit and treatment-by-visit interaction, stratification factors at randomization, and the continuous fixed covariates of baseline measurement. An unstructured variance covariance matrix will be used. Parameter estimation is based on the method of restrictive maximum likelihood (REML). MMRM will be the primary approach in the analysis of continuous variables.
- **ANCOVA-C:** For continuous efficacy variables that are collected at only one post-baseline visit (such as SES-CD), the missing data due to COVID-19 will be imputed using MI first before applying the ANCOVA model.

In addition, As Observed (AO) and Pattern Mixture Model (PMM) will be performed as sensitivity analysis, if appropriate, for categorical or continuous endpoints.

- **As Observed (AO):** The AO analysis will not impute values for missing evaluations, and thus a subject who does not have an evaluation on a scheduled visit will be excluded from the AO analysis for that visit. AO will include all values collected in the study regardless of censoring for steroids or not.
- **Pattern Mixture Model (PMM):** Subjects will be classified into pre-specified missing data patterns and the pattern variables will be defined based on these patterns. The random effect PMM⁵ approach will be performed, which includes the pattern variables in the model to examine the effect of missing-data patterns on the outcomes of interest. PROC GLIMMIX will be used in PMM approach for handling categorical endpoints, and PROC MIXED will be used for handling continuous endpoints. The model includes categorical effects of treatment, visit, treatment-by-visit interaction, missing-data pattern and treatment-by-pattern interaction, and the main stratification factors at randomization, and the continuous fixed covariates of baseline measurement, if applicable. The overall treatment effect can be estimated by averaging over the estimates from the different missing-data patterns.

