3.3 Other Efficacy Endpoint(s)

The primary and secondary efficacy endpoints are listed in Section 3.1 and Section 3.2, respectively. The additional efficacy endpoints for each induction period are:

12-Week Induction Period:

- Change from baseline in IBDQ at Week 4, Week 12 respectively
- Change from baseline in individual IBDQ domain scores (bowel, emotional, social, systemic) at Week 4, Week 12 respectively

- The achievement of IBDQ remission (IBDQ \geq 170 points) at Week 4, Week 12 respectively
- The achievement of IBDQ response (increase in IBDQ \geq 16 points from baseline) at Week 4, Week 12 respectively
- Change from baseline in WPAI-CD at Week 4, Week 12 respectively
- Change from baseline in European Quality of Life 5 Dimensions (EQ-5D-5L) at Week 4, Week 12 respectively
- Change from baseline in FACIT-Fatigue total score and individual items at Week 4, Week 12 respectively
- The achievement of increase in FACIT-Fatigue total score from baseline \geq 7 at Week 12
- The achievement of increase in FACIT-Fatigue total score from baseline \geq 9 at Week 12
- The achievement of increase in FACIT-Fatigue total score from baseline \geq 11 at Week 12
- Change from baseline in Short Form-36 (PCS and Mental Component Summary score [MCS] and all 8 domain scores) at Week 4, Week 12 respectively
- Change from baseline in Fecal calprotectin (FCP) at Week 4, Week 12 respectively
- Change from baseline in high-sensitivity C-reactive protein (hs-CRP) at Week 4, Week 8, Week 12 respectively
- Change from baseline in average daily AP score at Week 4, Week 8, Week 12 respectively
- Change from baseline in average daily SF at Week 4, Week 8, Week 12 respectively
- The achievement of clinical remission at Week 4, Week 8, Week 12 respectively
- The achievement of enhanced clinical response at Week 4, Week 8, Week 12 respectively
- The achievement of clinical response at Week 4, Week 8, Week 12 respectively

- Change from baseline in SES-CD at Week 12
- The achievement of a SES-CD ulcerated surface subscore ≤ 1 at Week 12 in subjects with a SES-CD ulcerated surface subscore ≥ 2 at baseline
- Patient Global Impression of Severity (PGIS) response at Week 4, Week 8, Week 12 respectively
- The achievement of subjects who report symptoms to be "Minimal" or "Absent" on the PGIS at Week 4, Week 8, Week 12 respectively, for subjects who did not report symptoms to be "Minimal" or "Absent" at baseline

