8.2.2 CD-Related Corticosteroid Therapy

The CD-related corticosteroids intercurrent event is defined as follows.

- Subjects not on CD-related corticosteroids (systemic or locally acting corticosteroids for CD) at baseline who initiated CD-related corticosteroids during the study;
- Subjects on CD-related systemic corticosteroids at baseline who have dosages increased to greater than the prednisone equivalent dose of corticosteroid taken at baseline, or initiation of any rectal corticosteroids during the study regardless of rectal corticosteroid dose;
- Subjects on CD-related rectal corticosteroids at baseline who have dosages increased to greater than the dose taken at baseline, or initiation of any new type of rectal or any systemic corticosteroids during the study.

The time point of the CD-related corticosteroids intercurrent event is defined as the earlier date when one or more of the scenarios above occurs for a subject. As such, all measurements at or after the occurrence of the CD-related corticosteroids intercurrent event through the end of the study will not be used in the analysis and will be handled as specified in [Appendix J](#).

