8.5 Secondary Efficacy Analyses

8.5.1 Key Secondary Efficacy Analyses

The estimands corresponding to the secondary efficacy endpoints are defined in Section 2.1. Details in estimand definition for the key secondary endpoints are outlined in [Appendix J](#).

In general, continuous secondary efficacy endpoints with repeat measurements will be analyzed using a MMRM model including factors for treatment group, visit, visit by treatment interaction, stratification variables and the continuous fixed covariates of baseline measurement. The MMRM analysis is considered primary for inferential purposes. Continuous secondary efficacy variables which are collected at only one post-baseline visit (such as SES-CD) will be analyzed using ANCOVA-C approach.

Categorical secondary efficacy variables will be analyzed using the CMH test controlling for stratification variables (prior biologics failed [0, 1, > 1] and baseline steroid use [Yes, No]), except for the endpoints related to draining fistulas and CD-related hospitalization. A CMH based two-sided 95% CI for the difference between each risankizumab treatment group and placebo group will be constructed. The endpoints of "The achievement of no draining fistulas at Week 12 in subjects with draining fistulas at baseline" and "Occurrence of CD-related hospitalization through Week 12" will be analyzed using Chi-square test (or Fisher's exact test if $\geq 20\%$ of the cells have expected cell count < 5).

The NRI-C method will be the primary approach for missing data handling for categorical secondary endpoints except for CD-related hospitalization and draining fistulas. The endpoint of "The achievement of no draining fistulas at Week 12 in subjects with draining fistulas at baseline" will be analyzed using NRI-NC as the primary approach due to the

small sample size. The endpoint of "Occurrence of CD-related hospitalization through Week 12" will be analyzed based on the observed data using AO approach only.

In addition, NRI-NC for missing data handling will be applied as sensitivity analyses for the binary secondary endpoints except for CD-related hospitalization and draining fistulas endpoints.

Analysis of PMM will also be performed as sensitivity analyses for ranked secondary endpoints as appropriate. Analysis of PMM will not be performed for the endpoint of "The achievement of no draining fistulas at Week 12 in subjects with draining fistulas at baseline" due to the small sample size.

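### The primary MMRM assumes one baseline slope for Weeks 4 and 12; adding the baseline-by-visit term before unblinding is a free improvement

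*SAP*

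**What the plan says.** SAP 8.3.2 gives the fixed effects of the MMRM as "the categorical fixed effects of treatment, visit and treatment-by-visit interaction, stratification factors at randomization, and the continuous fixed covariates of baseline measurement". On the covariance it adds: "An unstructured variance covariance matrix will be used". Section 8.5.1 restates the model for the ranked secondary endpoints, with "visit by treatment interaction, stratification variables and the continuous fixed covariates of baseline measurement", and gives it its role: "The MMRM analysis is considered primary for inferential purposes". Neither list has a baseline-by-visit term; treatment is the only effect allowed to change with visit.

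The model is fitted to observed values "after the CD-related corticosteroids censoring rule is applied". Under 8.2.2, "all measurements at or after the occurrence of the CD-related corticosteroids intercurrent event through the end of the study will not be used". Section 8.2.1, by contrast, keeps data collected after study drug is stopped.

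Section 3.3 schedules the relevant instruments at two post-baseline visits, for example "Change from baseline in IBDQ at Week 4, Week 12 respectively". FACIT-Fatigue, WPAI-CD and SF-36 have the same two visits. In 3.2, FACIT-Fatigue is ranked in both families (4th US, 5th global). IBDQ total (6th), WPAI-CD Overall Work Impairment (15th) and SF-36 PCS (16th) are ranked only in the global family. The pattern mixture model in 8.3.2 also enters baseline as a main effect.

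**The concern.** The plan lets the treatment effect and the covariance vary by visit but ties the baseline slope across visits. If baseline predicts the Week 4 and Week 12 values with different slopes, the fitted common slope is a compromise, and Week 12 is adjusted with the wrong one.

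With complete data this costs only precision. With missing Week 12 values it can cost more. For these endpoints the estimand in 2.1 is hypothetical with respect to steroid use, so the MMRM must in effect predict the removed Week 12 values from baseline and Week 4. Suppose removal depends on baseline or Week 4 status and is more frequent in one arm. The prediction error then does not cancel between arms.

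At stake are the Week 12 differences for ranked endpoints under type I error control, some of them early enough in the sequence to affect what is tested next.

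**Working it through.** **1. Inputs.** From the SAP: 342 versus 171 subjects per comparison (2.4), Weeks 4 and 12 (3.3), unstructured covariance (8.3.2). The SAP states no SD, baseline slope, or steroid or withdrawal rate by arm for these endpoints. Its power figures concern binary endpoints only. The main one (97% for 27.8% versus 12%) reproduces at 97.7% by exact enumeration of Fisher's test, but does not bear on this model. Everything below that is not in the SAP is an assumption.

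**2. Complete data, closed form.** Assume baseline SD 1, residual SDs 0.8 (Week 4) and 0.9 (Week 12), and residual correlation 0.6, so the residual covariance is 0.8 × 0.9 × 0.6 = 0.432. The common slope b weights the two true slopes by the column sums of the inverse covariance:

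- Week 4 weight = (0.81 − 0.432)/[(0.81 − 0.432) + (0.64 − 0.432)] = 0.378/0.586 = 0.645; Week 12 weight = 0.355.
- Variance inflation at Week 12 = 1 + (b12 − b)² × Var(baseline)/Var(residual at Week 12).
- Slopes 0.6 and 0.4: b = 0.529; inflation = 1 + 0.129²/0.81 = 1.021; standard error up 1.0%.
- Slopes 0.7 and 0.3: b = 0.558; inflation = 1 + 0.258²/0.81 = 1.082; standard error up 4.0%.

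The standard error with separate slopes is 0.9 × √(1/342 + 1/171) = 0.0843. Simulation gave 0.0843 to 0.0844 with separate slopes. With the shared slope it gave 0.0851 (slopes 0.6 and 0.4) and 0.0878 (0.7 and 0.3), in line with the formula. Bias was nil within noise.

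**3. With Week 12 loss.** Same model; loss (active/placebo) 5/15%, 8/25% or 10/35%. Bias is the shared-slope estimate minus the visit-specific one, in baseline SDs. Division by a standard error of about 0.091 gives the third column.

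| Condition | Bias (SD) | Bias (SE) | SE widening |
|---|---|---|---|
| Equal slopes, any loss mechanism | about 0 | about 0 | none |
| Slopes differ, loss unequal but unrelated to baseline or Week 4 | at most 0.002 | at most 0.02 | not tabulated |
| Slope change 0.1, loss related | 0.006 to 0.029 | 0.07 to 0.32 | 0.4% |
| Slope change 0.2, loss related | 0.012 to 0.060 | 0.13 to 0.66 | 1.0 to 1.7% |
| Slope change 0.4, loss related | 0.026 to 0.116 | 0.29 to 1.27 | 5 to 7% |

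The largest bias, 0.116, is an extreme corner: 35% placebo loss, driven by baseline in placebo only, with the slope more than halved (0.7 to 0.3). With the interaction, the estimate was unbiased within simulation noise (at most about 0.007 SD) throughout. When slopes were equal, its standard error was 0.0916 against 0.0915 without it.

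**4. On a points scale.** SD 11.5, true difference 0, Week 12 loss about 8-13% (risankizumab) versus 17-25% (placebo), loss likelier in sicker subjects. With a common SD, the baseline correlation equals the slope. Positive bias favours risankizumab.

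| Baseline correlation, Week 4 / Week 12 | Bias (points) |
|---|---|
| 0.7 / 0.4 | about +0.37, SE 4% wider |
| 0.7 / 0.6 or 0.6 / 0.5 | about +0.1 |
| 0.5 / 0.6 | about −0.1 |
| equal | none |

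Scale check, complete data: at Week 12 correlation 0.4 the standard error is 11.5 × √(1 − 0.16) × 0.0937 = 0.99, or 1.03 when 4% wider, and 0.37/1.03 = 0.36. At correlation 0.6 it is 11.5 × 0.8 × 0.0937 = 0.86, and 0.1/0.86 = 0.12.

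**5. Effect on a two-sided 0.025 test** (critical value 2.241; level chosen for illustration). A shift of 0.1 standard errors gives Φ(−2.141) + Φ(−2.341) = 2.6%. A shift of 0.35 gives Φ(−1.891) + Φ(−2.591) = 3.4%. Simulated rates were 2.4% to 3.5% for the planned model and 2.1% to 2.5% with the interaction. The Monte Carlo error is √(0.025 × 0.975/2000) = 0.35 percentage points, so only the top of that range stands out.

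**The case against.** A main-effect baseline covariate is a complete specification, used consistently across the MMRM and the pattern mixture model, and it contradicts nothing else in the SAP. It is a legitimate model, and the harm is conditional on facts the SAP does not report. Three stronger readings are tempting.

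- *That unequal steroid censoring or dropout biases the result.* It does not by itself. Slopes must also differ, and loss must depend on baseline or Week 4. That baseline predicts Week 4 better than Week 12 is a general expectation, not something in the SAP.
- *That the error favours risankizumab.* This holds only for a slope that falls over time with heavier loss among sicker placebo subjects. With a rising slope (0.5 to 0.6) the sign reverses, and the standard error was unchanged (0.901 in both models in one case, 0.932 in the other).
- *That type I error control fails.* At modest inputs the rate is close to nominal.

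Loss is also narrower than it may appear, because values after stopping study drug are kept. The as-observed analysis would show whether removed post-steroid values drive a result. However, it addresses a different estimand and does not relax the slope restriction.

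Most of this stands and limits the size of the point. It does not show any benefit from the restriction.

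**Conclusion.** The point holds as a free improvement. The text is clear that the deciding model for four ranked continuous endpoints imposes a common baseline slope, and no planned analysis isolates the effect of that choice. The possible consequence is a bias of unknown sign in the Week 12 difference, plus some lost precision.

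At the points-scale inputs the likely size is small: about 0.1 points for modest slope differences and about 0.4 for a large one. The wider grid shows it could be larger under harsher assumptions. All of these sizes rest on assumed SDs, correlations, loss rates and loss mechanisms. The documents do not support a claim that the planned estimates will be biased, only that they can be. The co-primary endpoints do not use this model, and in the US family only FACIT-Fatigue does.

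**What to change.** Before unblinding, add the baseline-by-visit interaction to the MMRM fixed effects in 8.3.2 and 8.5.1, and to the pattern mixture model for continuous endpoints in 8.3.2. The cost is one phrase in each place, one model term in the code, and one extra parameter per additional visit (one in total for Weeks 4 and 12). No visible precision is lost if the slopes turn out equal. The change should be pre-specified because these endpoints are under type I error control; added after unblinding, it would be post hoc.
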